1.1.2 Summary of Clinical data with EGT0001442

Clinical studies have been conducted to evaluate safety, tolerability, pharmacokinetics (PK), pharmacodynamics (PD), metabolism, and efficacy of EGT0001442. No deaths or study drug related serious adverse events (AEs) have been reported in the clinical trials. EGT0001442 up to 100 mg for up to 14 days was safe and tolerated in healthy volunteers. In a phase 2, double-blind, placebo-controlled study, subjects with type 2 diabetes mellitus were treated with EGT0001442 in doses of 5 to 50 mg or a placebo for 28 days. The most frequently occurring AEs were headache (4% in the placebo and 11% in the treatment groups), pollakiuria (none in the placebo and 4% in the treatment groups), fatigue (7% in the placebo and 2% in the treated group), and nausea (4% in the placebo and 3% in the treated group). No hypoglycemia was reported. Genital and urinary tract infections were observed in some subjects in the EGT0001442 treated groups, including balanitis candida, urinary tract infection, bacterial vaginitis, vulvovaginal candidiasis, and vulvovaginal mycotic infection.

Urinary glucose excretion (UGE) was measured in healthy and diabetic subjects. EGT0001442 increased UGE in a dose-dependent and saturable manner. The plateau in UGE corresponded to dosages of EGT0001442 above 20 mg/day. EGT0001442 treatment in subjects with T2DM for 4 weeks was effective in reducing FPG by 24 to 41.6 mg/dL in the

groups dosed with 5 to 50 mg/day EGT0001442. Subjects receiving EGT0001442 also had a reduction in body weight, blood pressure, and postprandial glucose compared to the changes in the placebo group. Details of the safety and efficacy information are described in the Investigator's Brochure

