The safety monitoring activities will include vital signs, physical examinations, urinalysis, adverse events, and concomitant medication use. The occurrence of blood, liver, or skin disorders will be monitored through laboratory testing and adverse event documentation.

Adverse event of special interests will include any clinical signs and symptoms indicating either upper or non-upper urinary tract infections (UTIs) and genital infections. Any adverse events that mapped to UTIs or genital infections must be documented.

DATA AND SAFETY MONITORING BOARD (DSMB)

An independent Data and Safety Monitoring Board (DSMB) will monitor the overall safety information during the EGT0001442 development. The safety review activity and potential risk benefit assessment will be defined in the charter.

MAJOR ADVERSE CARDIOVASCULAR EVENT ADJUDICATION

An independent cardiovascular adjudication committee is established to review the cardiovascular events during the study in a blinded fashion. These events include cardiovascular mortality, myocardial infarction, stroke, and hospitalization for acute coronary syndromes, urgent revascularization procedures, and, other possible serious cardiovascular events. The adjudicated events will be documented and archived to allow a meta-analysis to be performed to assess if there is any increase of cardiovascular risk to an unacceptable extent at the time of completion of all phase 3 clinical studies.

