6.9.7 Adverse event of special interest

6.9.7.1 Genitourinary infections

Events representing genitourinary infection (e.g. cystitis, urethritis, pyelonephritis, balanitis, vulvovaginitis should be carefully evaluated and documentation of signs, symptoms, infectious agent (bacterial or fungal), and treatment should be undertaken.

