6.9.7.2 Renal and urinary disorders

Events that may be related to the diuretic effect of an SGLT2 inhibitor (e.g. nocturia, pollakiuria, polyuria, and dysuria) should be carefully evaluated and documented.

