### 9.1.3 Adverse Events of Special Interest

Categories of adverse events of special interest (AESIs) include:

- Cardiovascular events: myocardial infarction, cerebrovascular stroke, acute coronary syndrome, cardiovascular death, new or exacerbated congestive heart failure, and etc.
- Hypoglycemic events
- Renal and urinary disorders: nocturia, pollakiuria, polyuria, dysuria, and etc.
- Genitourinary infection: cystitis, urethritis, pyelonephritis, balanitis, vulvovaginitis and etc.
- Liver related events.
- Cancer events.
- Bone fracture events.

All AESIs will be identified by appropriate MedDRA preferred term. A by-subject listing of each category of AESI will be produced. Additional information collected for hypoglycemic events including ADA severity and intervention will be tabulated and listed.

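### No planned output counts, by arm, the subjects with any genital infection, any upper UTI or any non-upper UTI, although Protocol 3.1 names all three as events of special interest

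*Protocol*

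**What the plan says.** The protocol describes these infections at two levels of detail.

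- **Protocol 3.1** (Other Safety Monitoring Activities) makes "any clinical signs and symptoms indicating either upper or non-upper urinary tract infections (UTIs) and genital infections" events of special interest. It names three entities and includes the symptoms that point to them. The action it asks for is limited: "Any adverse events that mapped to UTIs or genital infections must be documented".
- **Protocol 6.9.7.1** uses one category: "Events representing genitourinary infection (e.g. cystitis, urethritis, pyelonephritis, balanitis, vulvovaginitis should be carefully evaluated". Protocol 9.6.2.1 promises a summary of that category, plus a listing with signs, symptoms, infectious agent and treatment. The special-interest footnote in Appendix 1 also uses the single label.
- **Protocol 6.9.7.2** sets urinary symptoms apart: "Events that may be related to the diuretic effect of an SGLT2 inhibitor (e.g. nocturia, pollakiuria, polyuria, and dysuria". Protocol 9.6.2.4, the matching analysis section, cites 6.9.7.1 instead.

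SAP 9.1.3 follows the coarser level. Its categories include "Genitourinary infection: cystitis, urethritis, pyelonephritis, balanitis, vulvovaginitis and etc" and, separately, "Renal and urinary disorders: nocturia, pollakiuria, polyuria, dysuria, and etc". Membership is by MedDRA preferred term, but no term list is given. The output is stated as: "A by-subject listing of each category of AESI will be produced". Only hypoglycemia also gets a table. SAP 9.1.1 plans general tables of treatment-emergent events by system organ class and preferred term. SAP 10 records no changes to the planned analyses.

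**The concern.** Genital and urinary infections are the harm that the documents themselves lead one to expect. Protocol 1 cites an excess of both with another SGLT2 inhibitor, and Protocol 1.1.2 reports "balanitis candida, urinary tract infection, bacterial vaginitis, vulvovaginal candidiasis, and vulvovaginal mycotic infection" in subjects treated with EGT0001442. Four of those five terms are genital.

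A reader of the final report will want to know how many subjects in each arm had any genital infection, any upper UTI, or any lower UTI. No planned output answers this. The listing gives no counts. The preferred-term tables are too fine: balanitis and vulvovaginal terms each apply to one sex, and the trial enrols both, so no single term covers genital infection. The merged summary in Protocol 9.6.2.1 would be too coarse for a genital-only effect, and the SAP does not carry even that forward. A real difference could therefore sit unremarked across several small rows.

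**Working it through.** **The plan's own figures.** The documents give no rate, power or test for any infection. The only sample-size calculation is for HbA1c (Protocol 9.2, SAP 3.5): difference 0.4, SD 1.0, two-sided 5%, 90% power. The normal formula gives 2 × ((1.960 + 1.282) / 0.4)² = 131.3, so 132 per arm. The stated 131 (protocol) and 133 (SAP) give t-test power of 89.7% and 90.1%, so both reproduce. The figure used below is the 150 per arm to be enrolled.

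**Which output gives which count**

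| Source | Genital, upper and non-upper UTI separated? | By-arm count of subjects? |
|---|---|---|
| Protocol 3.1 | Yes | None; documentation only |
| Protocol 6.9.7.1 with 9.6.2.1 | No, merged | Summary promised, no test |
| SAP 9.1.3, Listing 14.3-8.1 | No, merged | None; listing only |
| SAP 9.1.1, Table 14.3-1.2 | Only as single preferred terms | Yes, term by term |

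Listing 14.3-8.1 reuses the layout of Listing 14.3-1.1, which has no column for infectious agent, signs or symptoms. The listing content promised in Protocol 9.6.2.1 is therefore also missing.

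**Illustration of the cost.** All infection rates here are assumptions. Power is by exact enumeration of two binomials with 150 per arm and a two-sided 5% pooled-variance (chi-square) test. With genital rate g and UTI rate u taken as independent, the merged rate is 1 − (1 − g)(1 − u). For example, at u = 6%, placebo is 1 − 0.99 × 0.94 = 6.94% and active is 1 − 0.94 × 0.94 = 11.64%. The ratio is 11.64 / 6.94 = 1.7 and the difference is 4.7 points.

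| Scenario | Placebo vs active | Risk ratio | Difference (points) | Power |
|---|---|---|---|---|
| Genital as one group | 1.00% vs 6.00% | 6.0 | 5.0 | 69% |
| Merged, UTI 3% in both arms | 3.97% vs 8.82% | 2.2 | 4.85 | 40% |
| Merged, UTI 6% in both arms | 6.94% vs 11.64% | 1.7 | 4.7 | 29% |
| Merged, UTI 10% in both arms | 10.90% vs 15.40% | 1.4 | 4.5 | 21% |
| Merged, UTI 3% vs 6% | 3.97% vs 11.64% | 2.9 | 7.7 | 71% |
| Merged, UTI 5% vs 8% | 5.95% vs 13.52% | 2.3 | 7.6 | 61% |
| Merged, UTI 6% vs 10% | 6.94% vs 15.40% | 2.2 | 8.5 | 65% |

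With genital infection at 1% vs 5%, power is 54% alone and 29%, 21% or 15% merged at the same three equal UTI rates.

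**Fragmentation.** Splitting 1% vs 6% evenly over two terms gives 0.5% vs 3% per term and 38% power for each. Over four terms it gives 0.25% vs 1.5% and 13% each. At an expected 1.5%, no single term would pass the >5% threshold of the common-event table, although the group at 6% would.

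**Upper UTI.** At an assumed 0.5% vs 2%, the expected counts are 150 × 0.005 = 0.75 and 150 × 0.02 = 3 subjects. Power is about 18% (about 4% with Fisher's exact test). A separate row is informative, but a test is not.

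**The case against.** A reader might infer more than the documents support, in four ways.

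1. **That the SAP dilutes a drug effect.** It does not: SAP 9.1.3 computes no merged rate, ratio or test. The dilution applies only to the merged summary in Protocol 9.6.2.1, which has no planned test either.
2. **That the SAP created the merge or labels urinary symptoms as diuretic effects.** The merge is in Protocol 6.9.7.1 with the same five example terms, and the diuretic wording is in Protocol 6.9.7.2 alone. Protocol 3.1 asks for documentation, not three analysis categories. The inconsistency starts inside the protocol.
3. **That pyelonephritis is hidden.** It keeps its own row in the preferred-term tables and its own entry in the listing.
4. **That merging always costs power.** The steep loss assumes equal UTI rates in both arms. The protocol's own background points to increases in both kinds of infection, and then merged power is close to that for genital infection alone. Even with equal UTI rates, the risk difference falls only from 5.0 to 4.5–4.85 points. Most of the loss is added noise.

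These points stand. Two further cautions also stand. Four genital terms out of five is a count of terms, not of events. The protocol reviewed is the February 2011 original, while the SAP refers to versions of April, August and September 2011, so the wording of 3.1 may have changed.

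The objection does not supply the missing count. Visible single terms are not a by-arm total, and the direction of any UTI effect is unknown in advance. That is a reason to show the groups both apart and combined.

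**Conclusion.** The point holds as a gap in the planned safety outputs. The protocol names three entities, then merges them. The SAP keeps the merge, replaces the promised summary with a listing, and declares no change. The only by-arm infection counts are for single preferred terms.

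The size depends on assumed rates. For a genital effect of 1% vs 6% with 150 per arm, a grouped count has about 69% power. Merging with an equal UTI rate of 3% to 10% gives 21% to 40%, and a single term gives 13% to 38% for an even split over four or two terms. If UTI rises too, merging gives 61% to 71%. No planned test is invalidated and the primary analysis is unaffected. What is at stake is whether an expected harm can be read from the report. It should be corrected before unblinding because it costs little.

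**What to change.** **SAP 9.1.3**
- Before unblinding, fix preferred-term lists for genital infection, upper UTI and non-upper UTI.
- Tabulate subjects by arm for each, with a risk difference and 95% confidence interval, and keep the combined genitourinary category beside them. Present upper UTI descriptively.
- Add infectious agent, signs, symptoms and treatment to Listing 14.3-8.1, as Protocol 9.6.2.1 promises, or record the departure in SAP 10.

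**Protocol**
- Align 6.9.7.1 and 9.6.2.1 with 3.1.
- Correct the cross-reference in 9.6.2.4, which cites 6.9.7.1 where 6.9.7.2 matches.

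**Urinary symptoms**
- Keep dysuria and pollakiuria under renal and urinary disorders. Flag them as possible UTI only where a positive urine culture is already recorded.
- Reconcile the culture provision. Protocol Appendix 1 sends urine for culture when the dipstick is positive for white cells or blood. Footnote 5 of the SAP schedule mentions a central-laboratory sample and an on-site dipstick but no culture, and the only culture field in the shells belongs to the NMP22 listing. Culture data may therefore not exist for every such case.

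**Cost.** SAP and protocol wording, three term lists, one table and one listing layout. The grouped counts need no new data. The symptom flag depends on which cultures were recorded. The downside is small counts per category.

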3.2 Rationale for Study Design and Control Group

THR-1442-C-418 is designed to evaluate the efficacy of EGT0001442 in the treatment of patients with T2DM. A randomized, double-blind study is the most suitable design and placebo is the appropriate control to evaluate a new agent in diabetic subjects. Diet and exercise counseling during the entire study will be provided to all participating subjects to reduce risks of worsening diabetic conditions. Monitoring plan based on SMBG, FPG, and HbA1c measurements as well as criteria to initiate rescue medications are included in the protocol to prevent prolonged hyperglycemia.

Results from published data in individuals with genetic mutations in the gene encoding SGLT2, subjects that have been treated with other SGLT2 inhibitors, and from previous clinical studies in healthy or diabetic subjects treated with EGT0001442 indicate that the risk of induced hypoglycemia as a consequence of the loss of SGLT2 activity should be minimal.

Reduction in HbA1c directly reflects improvement in glycemic control and is considered a well validated surrogate for the long-term microvascular complications of diabetes mellitus. Results from study THR-1442-C-402 demonstrated that 4 weeks of treatment resulted with a dose dependent reduction of 24 – 42 mg/dL FPG in subjects receiving EGT0001442 5 – 50 mg per day. Thirty (30) mg/ day of EGT0001442 dosage was chosen in the proposed study based on the near saturation of UGE and FPG decrease in previous clinical studies in healthy or diabetic subjects. Clinical data in the previous studies indicated that 30 mg/day EGT0001442 is well tolerated.

3.3 Study Duration and Dates

In the proposed study, diabetic subjects will be screened within 3 weeks of washout start. Eligible subjects who sign the written consent will receive placebo and start a 2 week run-in period prior to study drug administration. Subjects will receive 24 weeks of treatment for the main efficacy study and will continue for an additional 72 weeks for additional safety and efficacy study. All subjects will be followed for 1 week after the last dose. The overall study duration from screening until follow-up could last a maximum of 102 weeks for the study subjects. The duration of the overall study depends on the rate of patient accrual. For details of the schedule and nature of the investigations, see the Trial Activities Charts in Appendix 1

4 STUDY POPULATION SELECTION

4.1 Study Population

The study population will include approximately 300 subjects diagnosed with T2DM that are inadequately controlled by diet and exercise or by treatment with a single oral anti-diabetes agent and have the HbA1c between 7% and 10%. The study will recruit subjects from approximately 50 trial centers in 3 countries.

4.2 Inclusion Criteria

- 1. Male or female subjects ≥18 years old
- 2. Diagnosed with type 2 diabetes
- 3. Body mass index (BMI) \leq 37 kg/m²
- 4. HbA1c between 7 and 10% (inclusive) at screening based on an upper limit of normal for the HbA1c assay being 6.5±0.2 %
- 5. FPG <250 mg/dL at screening for subjects not treated with oral anti-diabetic therapies or FPG <240 mg/dL at screening for subjects treated with anti-diabetic therapies
- 6. Diabetes currently treated with diet and exercise only or diet and exercise along with one approved oral anti-diabetic agent
- 7. If taking anti-diabetic medication, dose and regimen must be stable for past 3 months
- 8. If taking antihypertensive medication, dose and regimen must be stable for past 3 months
- 9. If taking lipid modifying therapy, dose and regimen must be stable for past 3 months
- 10. Blood glucose <250 mg/dL based on finger stick blood glucose for all subjects at randomization
- 11. Subjects willing and able to comply with the investigational nature of the study and able to communicate well with investigators.
- 12. Able to comprehend and willing to provide written informed consent in accordance with institutional and regulatory guidelines.

4.3 Exclusion criteria

Subjects meet any of the criteria will be excluded:

- 1. Hemoglobinopathy that affects HbA1c measurement
- 2. Current use of injected therapy for treatment of diabetes (insulin or GLP-1 receptor based therapy)
- 3. Genitourinary tract infection within 6 weeks of screening
- 4. Greater than 2 episodes of genitourinary tract infection in the past year
- 5. History of kidney stones, bladder malfunction or other significant risk factor for urinary tract infections

Page 19 of 61

Confidential

- 6. eGFR, as calculated by the modification of diet in renal disease study equation (MDRD), < 50 mL/min/1.73 m² (Appendix 2)
- 7. Abnormal tests of liver function ALT, AST or bilirubin $\geq 3x$ ULRR
- 8. Diagnosed with proliferative retinopathy
- 9. Uncontrolled hypertension (blood pressure >150/95)
- 10. Not willing to use effective birth control if female with child-bearing potential
- 11. Female subjects who are pregnant or nursing
- 12. Life expectancy < 2 years
- 13. New York Heart Association (NYHA) Class 4 heart failure
- 14. Sera positive of HCV, HIV, or positive on drug screen
- 15. Currently participating another interventional trial
- 16. Not able to comply the study scheduled visits

5 STUDY TREATMENT(S)

5.1 Description of Treatment(s)

5.1.1 Study Drug

Theracos, Inc. will provide EGT0001442 tablets in one of the four different strengths as follows:

10 mg SR formulation (EGT0001442 SR Tablet, 10 mg)

15 mg SR formulation (EGT0001442 SR Tablet, 15 mg)

20 mg SR formulation (EGT0001442 SR Tablet, 20 mg)

20 mg IR formulation (EGT0001442 IR Tablet, 20 mg)

The SR tablet formulations consist of EGT0001442 (active pharmaceutical ingredient) and excipients including HPMC, lactose monohydrate, sodium bicarbonate, colloidal silicon dioxide and magnesium stearate in the 10, 15, and 20 mg dosages. The IR tablet formulation consists of 20 mg EGT0001442 (active pharmaceutical ingredient) and excipients including microcrystalline cellulose, lactose monohydrate, croscarmellose sodium, colloidal silicon dioxide, and magnesium stearate.

All study drug supplies will be prepared and labeled according to the requirements of local law and legislation and will be kept in a secure storage facility at controlled room temperature, 15 - 30°C (59 - 86°F). The pharmacist or designated CRO personnel will dispense the study drugs for each subject according to randomization assignment made in the IVRS.

5.1.2 Placebo

Theracos, Inc. will provide placebo tablets. The placebo control tablets consist of HPMC, lactose monohydrate, sodium bicarbonate, colloidal silicon dioxide and magnesium stearate.

Placebo will be prepared in white opaque tablets of the same size and appearance as the active drug tablets. All placebo supplies will be prepared and labeled according to the requirements of local law and legislation and will be kept in a secure storage facility at controlled room temperature, $15-30^{\circ}\text{C}$ ($59-86^{\circ}\text{F}$). The placebo control is packaged in a manner identical to the active drug product. The placebo tablets will be administered identically to the EGT0001442 tablets.

5.1.3 Rescue medications

Approved anti-diabetic medications will be provided to subjects who met the criteria to receive rescue medication due to poor glycemic control.

5.2 Treatments Administered

Study drug will be provided to the pharmacist in bottles of 45 tablets per bottle. Individual bottles of placebo will be provided for the run-in portion of the study. For the first 24 weeks of the study, subject kits will be provided and each kit will contain 4 bottles containing 45 tablets per bottle. For study weeks 25 - 96, subject kits will contain 2 bottles of 45 tablets. Study drug, EGT0001442 10, 15, or 20 mg tablets or matching placebo, will be dispensed by the pharmacy or designated study staff every 6 - 12 weeks. There will be no intra-subject dose escalation or back-titration.

Subjects who require rescue medication due to hyperglycemia will receive standard care for treating type 2 diabetes in addition to the study drug. The pharmacist will dispense the medications per investigator's prescription.

5.3 Selection and Timing of Dose for Each Patient

Dosing with either active drug or placebo will be based on randomized assignment. All study subjects will be instructed to self-administer one capsule prior to breakfast once daily and complete the dosing log. Subjects will be advised to take the study medication with a glass of water. The tablets will be swallowed without chewing.

On the day of scheduled clinic visits, subjects must fast for a minimum of 10 h prior to the visits at which blood samples will be drawn. During fasting, only water will be permitted. Subjects will be asked to record the meals they consume and the time that they last ate prior to blood draw for FPG and other laboratory testing.

5.4 Method of Assigning Patients to Treatment Groups

Eligible subjects who complete the 14 ± 3 day washout period to verify eligibility for the study and stability of their diabetes will be randomized to receive EGT0001442 or placebo according to a randomization code. Subjects are assigned to placebo or EGT0001442 at 30 mg/day in a 1:1 ratio. The random assignment of study subjects to treatment groups will be centrally located and managed utilizing an Interactive Voice Response Systems (IVRS). Randomization will be stratified by study center and based on screening HbA1c (≥ 7 to < 8.5% or ≥ 8.5 to 10%). This randomization protocol is designed to balance experimental treatments within each center and the baseline HbA1c.

The study will be conducted at multiple investigative sites and will likely involve variable numbers of subjects at each site. Enrollment will be on a competitive basis but will be capped at 30% of the total randomized subjects (90 subjects) from one center.

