A multinational, 2 arm parallel groups, randomized, double-blind placebo-controlled study to compare the treatment of once daily EGT0001442 at 30 mg with matching placebo in treatment-naïve type 2 diabetic patients (i.e. not taking an antihyperglycaemic agent for ≥16 weeks prior to study entry) or with diet and exercise in combination with one oral antidiabetes drug and an HbA1c of 7-10%. Approximately 300 eligible subjects will start a 2-week placebo run-in period prior to being randomly assigned to either once daily EGT0001442 or placebo in a 1:1 ratio for 24 weeks. Subjects with hyperglycemia may receive approved anti-diabetic medication. At week 24, subjects who have completed the main treatment period will continue to receive study drug until week 96. In the treatment

Confidential

•

extension period, subjects who have elevated HbA1c will have additional antidiabetic therapy added to the study drug consistent with treatment recommendations for type 2 diabetes.

Study Population and main eligibility criteria:

Approximately 300 patients that are inadequately controlled by diet and exercise or by treatment with a single oral anti-diabetes agent, randomized 1:1 to placebo and EGT0001442

- Type 2 diabetes per the American Diabetes Association criteria
- Male or female
- Age \geq 18 years
- Receiving one or no oral anti-diabetic agent and diet and exercise instruction
- HbA1c between 7 and 10% at screening
- Body mass index (BMI) $\leq 37 \text{ kg/m}^2$
- Fasting plasma glucose <250 mg/dL at screening for subjects not treated with oral anti-diabetic therapies
- Fasting plasma glucose <240 mg/dL at screening for subjects treated with antidiabetic therapies
- Fasting plasma glucose <250 mg/dL for all subjects at randomization

Test Product, Dose, and Mode of Administration:

EGT0001442 tablets 30 mg once daily by mouth

Reference Therapy; Dose; and Mode of Administration:

• Placebo – once daily by mouth

Duration of Treatment:

• 98 week (2wk run-in, 24 week primary evaluation, 72 week extension)

Statistical Methods:

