1.1.1 Summary of non-clinical data with EGT0001442

The potential adverse effects of EGT0001442 have been evaluated through safety pharmacology, genotoxicity, acute, chronic, and reproductive toxicity studies. Repeat dose toxicity studies performed in rats, dogs and monkeys found diarrhea and gastric irritation including sporadic ulceration, at the lowest observable effect level. The NOAELs based on these studies are 6.7 and 20 mg/kg/day in rats and monkeys, respectively, representing safety multiples of 8.1 and 19.6 relative to anticipated exposures in diabetic patients at the planned clinical dose of 20 mg/day. Chronic exposures produced similar toxicity profiles, with the additional finding of microvacuolization of renal cortical cells in monkeys after 39 weeks dosing. This microscopic pathology occurred without clinical chemistry correlates, and the renal effects generally reversed during the recovery phase. EGT0001442 does not affect fertility or in utero development up to the maximum tolerated doses in rats and rabbits. Details of the toxicology findings are described in the Investigator's Brochure.

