After the run-in period, approximately 300 subjects will complete the baseline assessment on day 1 after overnight fasting to confirm their eligibility. The subjects that remain eligible will be randomly assigned to one of the 2 treatment groups on day 1. Randomization will be stratified by study center and based on screening HbA1c (\geq 7 to <8.5% or \geq 8.5 to 10%). The planned doses are 30 mg/day of EGT0001442 or placebo. Each subject will be provided with study drug for 6 weeks, dosing instructions and log, diet and exercise counseling, and a diary card for recording food and fasting glucose information on the days prior to each clinic visit.

Each subject will be instructed to return to the clinic on weeks 2, 6, 12, 18, and 24 for safety monitoring and efficacy assessment including review of adverse events, concomitant medication, ECG, vital signs, physical examinations, testing of blood chemistry and hematology laboratory parameters, and a urinalysis.

Subjects who complete the 24-week treatment period will continue receiving the study drug for an additional 72 weeks. Subjects who receive rescue medication due to poor glycemic

control will continue to receive approved anti-diabetic medications and standard of care per investigator decision according to current treatment guidelines for 72 weeks. In the treatment extension period, subjects must return to the clinic on weeks 36, 48, 60, 72, 84, and 96 for continuous safety monitoring and efficacy assessment, including review of HbA1c values, adverse events, concomitant medication, ECG, vital signs, and physical examinations. A follow up exit visit will be conducted at 1 week after the last dose. Subjects will be advised to see their primary physician and resume standard of treatment to control diabetes.

GLYCEMIC CONTROL

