9.2 Determination of Sample Size

Approximately 300 patients will be enrolled and equitably allocated to receive either 20 mg/day EGT0001442 or placebo.

The sample size of 150 subjects per group was calculated based on the following assumptions:

- 1. This effect size is the mean difference between baseline and week 24. The active doses will decrease the HbA1c by 0.4%.
- 2. The placebo will not experience a substantive average decrease in mean HbA1c from baseline to week 24
- 3. The standard deviation of this difference is the same for both groups and is 1.0%.
- 4. The study design is balanced and the two-sided significance level for the hypothesis is 0.05.

Under the above assumptions, an evaluable sample size of 131 evaluable patients per treatment arm yields approximately 90% power that EGT0001442 treatment will be found to be significantly different from placebo. A sample size of 150 subjects per treatment arm will be enrolled to account for any subject lost-to-follow-up.

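### The protocol gives two test doses, 30 mg and 20 mg a day, and its supply instructions cannot deliver 30 mg

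*Protocol*

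**What the plan says.** Statements of 30 mg once daily:

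- Protocol synopsis, test product: "EGT0001442 tablets 30 mg once daily by mouth".
- Protocol 3.1: "The planned doses are 30 mg/day of EGT0001442 or placebo".
- Protocol 3.2, which also gives a rationale: "Thirty (30) mg/ day of EGT0001442 dosage was chosen in the proposed study".
- Protocol 5.4, the operative assignment: "Subjects are assigned to placebo or EGT0001442 at 30 mg/day in a 1:1 ratio".

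Statements of 20 mg/day:

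- Protocol 9.2: "Approximately 300 patients will be enrolled and equitably allocated to receive either 20 mg/day EGT0001442 or placebo".
- Protocol 1.1.1, where rat and monkey safety multiples of 8.1 and 19.6 are given "relative to anticipated exposures in diabetic patients at the planned clinical dose of 20 mg/day".

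Supply and administration:

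- Protocol 5.1.1 provides "EGT0001442 tablets in one of the four different strengths as follows": 10, 15 and 20 mg sustained-release and 20 mg immediate-release. Section 5.2 likewise lists 10, 15 or 20 mg. There is no 30 mg tablet.
- Protocol 5.3 tells subjects to take one unit before breakfast once a day. It calls that unit a capsule in one sentence and a tablet shortly afterwards.
- Protocol 5.2, for the first 24 weeks: "each kit will contain 4 bottles containing 45 tablets per bottle". Extension kits hold two such bottles. Section 5.9.1 says the 45 tablets include 3 spare.
- Protocol 3.1 gives each subject a 6-week supply at randomization, and 5.5 refers to one drug kit per subject at that point.

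SAP sections 3.1, 3.4 and 3.5 give only 20 mg, and describe capsules.

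**The concern.** There is one active arm, and section 5.2 rules out changing a subject's dose during the study. The two figures therefore cannot be two arms or two titration steps; they are two statements of the same regimen. The 20 mg figure is also more than a single stray number: it appears in two sections, and the strengths, the dosing instruction and the bottle counts all fail to match 30 mg.

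The dose defines the intervention. As written, it is unclear which regimen the Week 24 comparison estimates and which one the assumed 0.4% HbA1c reduction refers to. The section 1.1.1 multiples are stated for a dose other than the one assigned in 5.4. An ethics committee or site working from this text could not tell which dose it was approving or dispensing.

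**Working it through.** **1. The plan's own figure.** Section 9.2 gives 131 evaluable patients per arm for about 90% power, with a difference of 0.4, SD 1.0 and two-sided alpha 0.05.

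- Normal approximation: n = 2 x (1.960 + 1.282)² x (1.0/0.4)² = 131.3 per arm, rounded up to 132. The t-test calculation gives 132.3, rounded up to 133, which is the figure in SAP 3.5.
- Power at 131 per arm: 89.9% (normal) or 89.7% (t-test).

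The stated figure reproduces. Dose is not an input, so the conflict in 9.2 lies in the dose label and not in the arithmetic.

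**2. What the bottle counts imply.** Net tablets per bottle: 45 - 3 = 42, which is 6 weeks at one a day.

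| Period | Net tablets | Days | Units per day |
|---|---|---|---|
| Weeks 1-24, one kit | 4 x 42 = 168 | 24 x 7 = 168 | 1 |
| Extension, one kit per 12 weeks | 2 x 42 = 84 | 12 x 7 = 84 | 1 |

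The extension row assumes the same overage per bottle. The protocol's Schedule of Events agrees: drug is dispensed at weeks 0, 6, 12 and 18 (four bottles for 24 weeks) and then every 12 weeks from week 24. One unit a day delivers 10, 15 or 20 mg.

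**3. What 30 mg would need over 168 days.** The total is 30 x 168 = 5040 mg. A 180-tablet kit, overage included, holds at most 180 x 20 = 3600 mg.

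| Route to 30 mg | Units per day | Units for 24 weeks | Share covered by 180 | Kit lasts |
|---|---|---|---|---|
| 2 x 15 mg, or 10 + 20 mg | 2 | 336 | 53.6% | 90 days |
| 3 x 10 mg | 3 | 504 | 35.7% | 60 days |
| 1.5 x 20 mg (splitting not described) | 1.5 | 252 | 71.4% | 120 days |

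The coverage figures assume one kit per subject for the 24 weeks. Independently of that assumption, every route conflicts with the one-unit instruction in 5.3.

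**4. Safety multiples.** The documents give no exposure by dose, so only an assumed range can be shown for 30 mg. If exposure did not rise above that at 20 mg, the multiples stay at 8.1 (rat) and 19.6 (monkey). If exposure rose in proportion to dose, they become 8.1 x 20/30 = 5.4 and 19.6 x 20/30 = 13.1.

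**5. Effect on HbA1c.** No HbA1c results by dose are given, so a difference between 20 and 30 mg cannot be derived. Section 1.1.2 places the plateau in urinary glucose excretion above 20 mg/day, which does not settle the question.

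**The case against.** The strongest objection is that the conflict may already have been removed. The protocol under review is the original of 02 February 2011. The SAP, final on 22 November 2011, cites Amendment 1 of 11 April 2011, and its table shells list protocol versions dated 11 April, 18 August and 12 September 2011. It uses one dose throughout. This limits what can be said about the trial as later run, but it does not reconcile the protocol text supplied. SAP section 10 reports no changes, but it does not say which protocol version it was compared with, so it is weak evidence either way. The finding does not rest on the SAP.

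A second objection is that one kit per subject for 24 weeks is an inference. Section 5.2 does not state it, and section 5.11 mentions resupply. This is fair, and the coverage percentages depend on it. The inference is nevertheless well supported by the 6-week supply at randomization, the four dispensing visits and the overage per bottle, and no passage provides for issuing extra kits. Even without it, one unit a day of at most 20 mg cannot make 30 mg. The 10 + 20 mg route is also doubtful if 5.1.1 means a single strength per subject.

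Third, the statistical machinery is untouched. That is correct for the sample size, the primary t-test and the SAP's exposure duration. Compliance under SAP 8.2, a unit count, would change only if the intended number of units per day is not one.

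**Conclusion.** The concern holds. The protocol's current text states two doses for one arm: 30 mg in the synopsis, 3.1, 3.2 and 5.4, and 20 mg in 9.2 and 1.1.1. The assignment in 5.4 cannot be carried out with the strengths and the one-unit instruction given, and the bottle counts corroborate one unit a day. Confidence is high for this protocol text; whether a later version corrected it cannot be seen from the documents supplied.

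The contradiction must be fixed because the dose identifies the treatment being tested, the regimen behind the assumed 0.4% effect and the basis of the safety multiples. It does not change the sample size or the primary test. The kit shortfall rests on one kit per subject, and the 30 mg safety multiples rest on the assumed exposure range. Neither is needed for the main conclusion.

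**What to change.** 1. Reconcile dose, tablet strength, units per day, dosage form (tablet or capsule) and bottle counts across the protocol synopsis and sections 1.1.1, 3.1, 3.2, 5.1 to 5.4, 5.9.1 and 9.2. State how many kits each subject receives.
2. State in section 9.2 which dose the assumed 0.4% HbA1c effect refers to.
3. Give the section 1.1.1 safety multiples at the reconciled dose, based on exposure data.
4. Confirm that SAP 3.1, 3.4, 3.5 and 8.2 agree. If the dose or dosage form was amended, record that in SAP section 10.

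The cost is wording changes and a check of the supply plan, with no additional patients. Which dose is right is for the sponsor to establish.
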